7.1.1.2 Tacrolimus (Prograf®)

Tacrolimus (Prograf®), or generic equivalent, will be administered to attain target trough levels outlined in Table 3. Suggested dosing is outlined in Table 2.

Timepoint	Tacrolimus Dose
Post-operatively (by 72 hours following transplant operation) *	0.01-0.04 mg/kg/day IV continuous infusion OR 0.06-0.1 mg/kg/day (maximum 5 mg per dose) via NG or G-tube divided into 2 equal doses OR 0.08 mg/kg/day sublingual divided into 2 equal doses
Once taking PO	0.1-0.3 mg/kg/day PO divided into 2 equal doses
*Dosing may be adjusted to every 8 hours in infants and young children if therapeutic levels are hard to achieve (due to rapid metabolism of the drug in this age group).	

Table 2: Tacrolimus Dose

Dosing may be adjusted for underlying medical conditions and/or interactions with other medications.

Target whole blood tacrolimus concentrations are as follows:

Timepoint	Target Trough Level After Transplant
First 2 Weeks Post-Transplant	10-20 ng/mL
Week 2-1-year Post-transplant	10-15 ng/mL
After 1 Year	6-10 ng/mL
The above given recommendations for therapeutic drug monitoring of tacrolimus may not be suitable for infants secondary to the different pharmacokinetics in infants.	

Table 3: Tacrolimus Trough Levels

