8.4. Study Assessments

Subjects enrolled in this study will be followed for a minimum of 12 months post-transplant. Follow up visits will continue as detailed in Appendix 1 until the last participant completes 12 months of follow up (up to 54 months). Subjects may have blood and BAL samples collected at the following timepoints post-transplant:

- Transplant/Randomization-Day 0
- Day: 12
- Weeks: 4-6
- Months: 2, 3, 6, 9, 12, 18 and 24

Clinical safety will be monitored through routine physical examinations and appropriate laboratory assessments. During this period participants will have repeated clinical/laboratory evaluations, as specified in the Schedule of Events (Appendix 1, Schedule of Events- Recipient).

Assessments for the development of adverse events, serious adverse events, infections, rejections, death, PTLD, relisted for transplant or re-transplantation and hospitalizations will be completed at each study visit. All events will be reported using a designated electronic case report form (eCRF).

Chronic allograft dysfunction, relisting for transplant and death data will be collected up to 54 months post-transplant.

Protocol Biopsies

Transbronchial biopsies will be performed routinely as part of standard of care. The histologic evaluations from routine biopsies at day 12, week 4-6, month 3, month 6, month 12, month 18, and at the time of a symptomatic episode will be evaluated by the local pathologist and interpretations recorded on electronic case report forms (eCRFs).

Tacrolimus Standard Deviation Marker

Variability of tacrolimus will be monitored continuously starting 3 months post-transplant, using the calculation of the degree of fluctuation of tacrolimus blood levels over time, described by the standard deviation (SD) of tacrolimus levels.⁸² All outpatient levels obtained at least 3 months post-transplant will be used. In order to ensure the validity of tacrolimus trough levels, clinical sites will agree on quality control measures for obtaining trough levels. A rolling SD will be calculated for every patient using 1-year of tacrolimus levels (at least 3 trough levels). A SD of 2.0 or more (Shemesh et al. manuscript in preparation), an undetectable level or the absence of a tacrolimus trough level for 3 months will trigger a phone call among the site coordinator, the participant, parent(s)/guardian(s) and trained personnel at ISMMS to address barriers to adherence.

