Individuals who meet the criteria listed below will not participate in the phone calls for the tacrolimus standard deviation marker:

1. Inpatient status
2. Any condition that, in the opinion of the investigator, may impact the quality or interpretation of the data obtained from the intervention.

The frequency of the calls is described in the table below.

Timepoint (following SD of 2.0 or more or undetectable level)	Call Frequency
Month 1	Weekly
Month 2	Monthly
Month 3-Month 24	Every other month

Table 10: Tacrolimus Standard Deviation Marker Call Schedule

Per the center clinician's discretion, calls may be escalated to 2 times per week for up to 1 month at any time during the intervention.

After one month, calls may revert to a weekly schedule for the following reasons:

- Participant discloses continuing non-adherence during the call;
- The most recent trough level is “undetectable”;
- The parent/guardian and/or team are concerned about ongoing non-adherence;
- A deterioration in medical outcomes as determined by the Center that is not explained by physiological factors;
- Per the clinical discretion of the call center staff member (i.e., the call center and parents/guardians are working on a remedy to an identified barrier).

The team at the call center will determine when the participant will return to the schema outlined in **Table 10**.

With the consent of the participant, information obtained during the intervention will be shared with the participant’s parent(s)/guardian(s) and clinical team.

Neurological Assessment

All participants who receive at least 1 dose of Rituximab (Rituxan®) or placebo will undergo a screening neurological exam at the time points specified in Appendix 1. Subjects who have objective findings will be evaluated by their local Neurology consult service.

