7.3.1. Post-transplant Clinical Endpoints

Variable: Secondary incidence endpoints including:

- Chronic allograft dysfunction, defined as indicated for the primary endpoint
- Listing for re-transplant, defined as indicated for the primary endpoint
- Death, defined as indicated for the primary endpoint
- Primary Graft Dysfunction (PGD), defined at 0, 24, 48, and 72 hours post-transplant per Section 7.5.4 of the protocol
- Grade A Acute Rejection, reported locally as defined in Section 7.5.1 of the protocol

- Antibody Mediated Rejection of Grade II or III, reported locally as defined in Section 7.5.2 of the protocol
 - Additionally, if the data allow, AMR will be evaluated according to the 2016 ISHLT consensus guidelines published in the Journal of Heart and Lung Transplantation.

Analysis: For each of the above incidence endpoints, the proportion of subjects with events will be reported by treatment group with a corresponding 90% confidence interval, and for PGD and the rejection endpoints the treatment groups will be compared using a Chi-square or Fisher's Exact test. The incidence of grade 2 or higher PGD will be summarized overall and at each of the 4 time points separately. Additionally, for acute rejection and antibody mediated rejection, number of events per person time (e.g., year) will be estimated.

An example of SAS code to be used:

```
Proc freq;  
  tables treatment_group * endpoint / chisq measures cl alpha=0.1;  
run;
```

Variable: Incidence of meeting the tacrolimus variability threshold

Analysis: Among subjects who have at least 3 outpatient tacrolimus trough levels collected that are at least 3 months (i.e., greater than or equal to 3 months) post-transplant, an estimate of the standard deviation of tacrolimus levels will be produced for each subject. This estimate will be a rolling estimate (continually re-assessed) and may use up to 1 year worth of trough levels at any given time. The proportion of subjects with an estimated standard deviation at any time of 2.0 ng/mL or greater will be reported with a corresponding 90% confidence interval.

Variable: Incidence of completion of the Tacrolimus Variability Intervention (TVI)

Analysis: Among subjects who qualified for and agreed to participate in the TVI, the proportion of subjects who complete the intervention will be reported with a corresponding 90% confidence interval.

Variable: Magnitude of change in standard deviation of tacrolimus levels following intervention

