Analysis: Among subjects who qualified for and agreed to participate in the TVI, the change in standard deviation of tacrolimus levels following the TVI will be examined. More specifically, a paired t-test will be carried out using the pre-intervention and post-intervention estimates of the standard deviation. An estimate of the mean difference between pre- and post-intervention standard deviation with a corresponding 90% confidence interval and p-value will be produced.

The value used for pre-intervention may be the same estimated standard deviation which qualified the subject for the TVI; however, if additional tacrolimus levels are recorded for a subject prior to their re-affirmation of consent for TVI participation, all outpatient tacrolimus levels in the year prior to commencement of the TVI will be used for estimating the pre-intervention standard deviation.

Likewise, the standard deviation value used for post-intervention will be estimated using all outpatient tacrolimus levels collected in the 180 days following completion of the TVI.

All estimates of the standard deviation pre- or post-intervention will adhere to the same conditions described earlier, which mandate at least 3 outpatient tacrolimus levels collected at least 3 months post-transplant.

Additionally, the change in standard deviation will be analyzed using the same paired t-test approach for pre-intervention vs. 180 days post-enrollment into the TVI, providing an assessment of change during the intervention.

Furthermore, attempts will be made to identify a set of “control” subjects for descriptive comparisons to subjects who enrolled and completed the TVI. These “control” subjects will at a minimum consist of subjects who qualified for but did not enroll in the TVI, and may be supplemented with subjects whose standard deviation exceeded 2.0 ng/mL but were not flagged due to enrollment in the TVI having been terminated. No formal statistical comparison of these two sets of subjects is planned.

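### The rolling tacrolimus SD can reach 2.0 ng/mL because the target trough is lowered at 1 year, and the paired pre/post test may use as baseline the SD that selected the child

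*SAP*

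**What the plan says.** **Threshold.** The Protocol's study definitions set the tacrolimus variability threshold as an SD of 2.0 or more on outpatient troughs, or an undetectable trough. Protocol 8.4 computes a rolling SD on 1 year of outpatient levels from month 3, with at least 3 levels. SAP 7.3.1 keeps that window and states "The proportion of subjects with an estimated standard deviation at any time of 2.0 ng/mL or greater will be reported". Neither document splits or centres the levels at month 12.

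**Targets.** Protocol Table 3 (7.1.1.2) gives 10-15 ng/mL for "Week 2-1-year Post-transplant" and 6-10 ng/mL after 1 year. Its note adds that the recommendations "may not be suitable for infants secondary to the different pharmacokinetics in infants".

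**Entry to the tacrolimus variability intervention (TVI).** Besides the SD, Protocol 8.4 says "an undetectable level or the absence of a tacrolimus trough level for 3 months will trigger a phone call". The last row of the call schedule (Table 10) is "Month 3-Month 24".

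**Change in SD.** In SAP 7.3.1, "a paired t-test will be carried out using the pre-intervention and post-intervention estimates of the standard deviation", with a mean difference, 90% CI and p-value. "The value used for pre-intervention may be the same estimated standard deviation which qualified the subject for the TVI"; if further levels exist before consent is re-affirmed, all outpatient levels in the year before TVI start are used. The main post value covers the 180 days after TVI completion; an additional contrast uses 180 days after TVI enrollment. Descriptive controls are at least the children who qualified but did not enroll, possibly supplemented by children above 2.0 ng/mL who were not flagged because TVI enrollment had ended. No formal comparison with them is planned.

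**The concern.** An SD over a window that contains a planned change of target measures that change as well as erratic levels. A child who follows the protocol closely could be counted as variable.

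The change analysis has a different problem. A child who enters because an estimated SD was high will tend to show a lower estimate next time, whatever the phone calls do. A one-group paired test against that same SD reads this as a fall.

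At stake is the interpretation of secondary endpoints under a feasibility objective: threshold incidence, change in SD and, through its denominator, TVI completion. No trial decision rests on them.

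**Working it through.** The documents give no expected rate, sample size or power for these endpoints, so there is no plan figure to reproduce.

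**A. Pooling two target ranges**

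Inputs from Table 3: midpoints 12.5 and 8.0 ng/mL, a shift of 4.5. For a child with no other variation, n levels in the window, k of them after the change and a drop of d:

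SD = d × √[k(n−k) / (n(n−1))]

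- 12 levels, 3 after the change: 4.5 × √(27/132) = 2.04.
- 12 levels, 6 after the change: 4.5 × √(36/132) = 2.35.
- Largest factor: 0.577 for 3 or 4 levels and 0.522 for 12. The drop needed to reach 2.0 is 2/0.577 = 3.46 to 2/0.522 = 3.83 ng/mL.
- A child at the same relative position q (0 to 1) in both ranges goes from 10+5q to 6+4q, a drop of 4+q, and so crosses.
- Counter-cases: steady 11 then 9 gives at most 0.577 × 2 = 1.15; 12 then 9 at most 0.577 × 3 = 1.73.

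Percentage of always-in-target children crossing by month 24, by simulation. Sampling frequency and level patterns are assumptions. Follow-up is taken as uniform over 12-54 months, so (54−24)/42 = 71% reach month 24.

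| In-target pattern | Monthly | 2-monthly | 3-monthly | Visits only |
|---|---|---|---|---|
| Uniform within range | 95 | 93 | 87 | 74 |
| Same, no target change | 19 | 22 | 28 | 25 |
| Steady, same relative position (within-child SD 0.5) | 91 | 92 | 89 | 81 |
| Steady, independent positions | 62 | 66 | 65 | 60 |
| Lower half of first range, then upper half of second | 0 | 0 | 4 | 7 |

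With no target change, the last three patterns give 0%.

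**B. Baseline chosen because it was high**

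Take a child with true SD 1.5 and 3 levels. P(estimate ≥ 2.0) = P(χ² on 2 df ≥ 2 × 4/2.25 = 3.56) = exp(−1.78) = 0.17 at one look, and there are repeated looks. If flagged, the baseline is at least 2.0 while later estimates are centred near the true value.

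Simulation with no intervention effect and no target change. Assumptions: monthly draws from month 3; first crossing by month 24; true SD lognormal between children (log-SD 0.4); post value from the next 6 months; 10 children; two-sided test at 0.10, so 5% false falls expected.

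| Median true SD | 1.0 | 1.5 | 2.0 | 2.5 | 3.0 |
|---|---|---|---|---|---|
| False fall, qualifying SD as baseline (%) | 85 | 54 | 34 | 18 | 12 |
| False fall, 2 levels added to baseline (%) | 67 | 38 | 23 | 15 | 10 |

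Repeat runs agree to about 2 points. At median 3.5 the first row falls to 8%. Over medians 1.0 to 3.5, or levels uniform within range, the mean null change after enrollment is −0.15 to −0.89 ng/mL.

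Adding the target change (medians 1.0 to 2.5, or uniform) moves the mean post-enrollment change to between −0.01 and −1.61. In children flagged by month 12, whose post window can span the change, it is −0.91 to +0.50, so the two effects can add or offset.

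Evaluability of the main contrast: if completion means the 24 months of Table 10 (an inference; neither document defines it), a child flagged at month 6, 12, 15 or 24 needs 36, 42, 45 or 54 months of follow-up. Under uniform accrual, 50 × (54−T)/42 gives at most about 21, 14, 11 or 0 children, before refusals. With 3-monthly draws, 180 days hold fewer than the required 3 levels.

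**C. SAP against protocol**

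| Item | Protocol | SAP 7.3.1 |
|---|---|---|
| Threshold | SD limb or undetectable level (study definitions) | SD limb only |
| Change in SD | Between-arm ANCOVA (13.4.4) | One-group paired t-test |
| Completion denominator | Those meeting the threshold (synopsis); those identified to participate (13.2) | Those who qualified and agreed |

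**The case against.** The strongest reply is that the SAP reports the SD limb as the protocol defines it, sets no alpha for the paired test, describes the post-enrollment contrast only as change during the intervention, and plans descriptive controls. The causal reading would be the reader's. Much of this stands and limits the severity. It does not remove the point: a p-value and 90% CI are still produced, nothing warns of regression to the mean, and the controls are not tied to that result.

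Four stronger readings are tempting but not supported:

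- That most in-target children will be falsely counted. Table 3 gives targets, not achieved levels; the scenarios run from 0% to 95%; the effect needs follow-up past month 12; and the table carries its own caveat for infants.
- That TVI children enter mainly through the SD. Protocol 8.4 lists three triggers and gives no shares. Children called only for an undetectable or absent level are not selected on SD.
- That the SAP wrongly ignores children with no level for 3 months. The threshold definition does not include absent levels, and qualifying for the TVI can be read to cover every trigger in 8.4.
- That the missing relative risk and risk difference are a tacrolimus defect. SAP 7.3.1 specifies neither for any incidence endpoint.

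The undetectable limb usually changes little: one zero among 12 levels already gives m/√12, which is 3.61 with the others at 12.5 and 2.31 with the others at 8. The protocol's own completion denominators already differ from each other.

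**Conclusion.** The point holds in this form. Windows spanning month 12 can count the planned target change as variability: certainly for a steady child whose level drops by about 3.8 ng/mL or more with 3 to 12 levels well split across the change, and not at all for small drops. For children who enter through the SD trigger, the paired change is biased towards a fall. The bias is severe if true SDs lie below or near 2.0 and slight if most lie well above it. The closed-form results need only Table 3 and the SD formula. The percentages rest on assumed sampling, spread and group size, and the documents cannot say where in the range this trial falls. The unexplained SAP departures are a matter of reading. Severity is minor to moderate.

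**What to change.** In the SAP:

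1. Keep the raw SD of 2.0 ng/mL as reported, since it was the live trigger. Split the incidence into crossings in windows inside one target period and crossings only in windows spanning month 12. As a supportive analysis, add an SD computed within one target period, or on deviations from the target midpoint in force at each draw, without claiming that 2.0 applies to a centred SD.
2. Label the paired pre/post change descriptive, state that regression to the mean is expected, and do not use its p-value or 90% CI as evidence of a TVI effect. Define completion. Show the same change over matched windows in both control groups already foreseen: children who qualified but did not enroll, and children above 2.0 who were not flagged because TVI enrollment had ended. The second group is less self-selected, so make its use firm rather than optional.
3. Reconcile SAP and protocol on the undetectable-level limb, the completion denominator and the between-arm ANCOVA, or give the reason for each change. The ANCOVA tests rituximab, not the calls.

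The cost is wording and programming on data already collected. Single-period windows hold fewer levels around month 12, and the control groups will be small. Centring alone does not rescue the paired test, because the selection remains.

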Antibody Mediated Rejection	
Antibody Mediated Rejection (AMR) will be defined based on the Revision of the 1996 Working Formulation for the Standardization of Nomenclature in the Diagnosis of Lung Rejection and the Pathology of pulmonary antibody mediated rejection and the 2012 update from the Pathology Council of the ISHLT.^{103,104} AMR will be diagnosed based on the presence of one or more of the following:
 
 • Donor Specific Antibody (DSA) or autoantibody; • Abnormal Histology; • Graft Dysfunction.
Anonymized	
A sample that was previously identifiable, has had all identifiers removed and can no longer be linked back to the subject or the subject's medical record by any means.

Chronic Allograft Dysfunction	
Chronic allograft dysfunction will be diagnosed locally based on ISHLT criteria for BOS or histologic evidence of obliterans bronchiolitis.^{103, 105} Local sites will rule out acute rejection, acute infection and airway stenosis or narrowing prior to diagnosing chronic allograft dysfunction.

Donor Specific Antibodies or Autoantibodies	
Circulating antibody to HLA or other antigens expressed on donor endothelial cells.

Inadequate Weight Gain	
Drop between 5-10 percentile points

Infectious Events	
Infectious events will be defined using published criteria from the ISHLT.¹⁰⁶ The 2010 guidelines on defining infections in cardiothoracic transplantation provide classification of bacterial, fungal and viral pulmonary infections in lung transplant recipients.

Lost to Follow-Up	
The CTOTC-08 subject may be considered "lost to follow up" after the subject misses a minimum of 3 consecutive study visits, and the site personnel has made a number of unsuccessful phone contacts. The decision to early terminate the subject will be the decision of the site PI, all attempts to establish contact with the subject will be documented in the study files.

Tacrolimus Variability Intervention	A series of calls with the participant, parent(s)/guardian(s) and specifically trained call center personnel to address barriers to adherence, using a manualized intervention.
Tacrolimus Variability Threshold	SD of 2.0 or more (outpatient tacrolimus trough levels) or an undetectable tacrolimus trough level.
Primary Graft Dysfunction	PGD is defined according to the recent summary statement from the ISHLT and will be graded from 0 to 3 based on radiographic changes and the ratio of PaO ₂ /FiO ₂ . ¹⁰⁷

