1. PROTOCOL SYNOPSIS

Title	B cell Targeted Induction to Improve Outcomes in Pediatric Lung Transplantation
Clinical Phase	Phase 2
Number of Sites	7 US Sites
IND Sponsor/Number	NIAID/IND Number 121403
Primary Study Objective	To determine whether rituximab induction along with standard of care immunosuppression will improve outcomes following pediatric lung transplantation.
Secondary Study Objectives	
 1. To determine the effects of rituximab induction on post-transplant immunity in pediatric lung transplant recipients. 2. To assess the safety and tolerability of rituximab. 3. To assess the feasibility of a phone based intervention to decrease tacrolimus trough level variability.
Study Design/Treatment Description	Phase 2, prospective, multi-center, double-blind, randomized, placebo-controlled clinical trial in which 50 primary pediatric lung transplant recipients will be randomized (1:1) to receive either induction therapy with anti-CD20 mAb (375 mg/m ²) IV or placebo (IV day 0 and day 12 post-transplant) plus standard of care immunosuppression (thymoglobulin induction, tacrolimus or generic equivalent, MMF or generic equivalent, and steroids).
Primary Endpoint	
The primary endpoint is a composite of the earliest time to any of the following events during the follow-up period:
 
 • Chronic Allograft Dysfunction • Listed for Retransplant • Death
Secondary Clinical Endpoints	
 1. Post-transplant clinical outcomes including: 
 a. Incidence of chronic allograft dysfunction, listing for retransplantation, and death during the follow-up period, which will be a minimum of 12 months post-transplant b. Incidence of Primary Graft Dysfunction c. Incidence of Grade A Acute Rejection during the follow-up period, which will be a minimum of 12 months post-transplant d. Incidence of Antibody Mediated Rejection during the follow-up period, which will be a minimum of 12 months post-transplant e. Incidence of tacrolimus variability threshold during the follow-up period, which will be a minimum of 12 months f. Percentage of participants meeting tacrolimus variability threshold who complete tacrolimus variability intervention

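### SAP 7.3.1 narrows two tacrolimus endpoints: intervention completion is computed only among those who agreed, and threshold incidence leaves out an undetectable level as a criterion

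*SAP*

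**What the plan says.** **Threshold.** The protocol's Study Definitions page defines the tacrolimus variability threshold as "SD of 2.0 or more (outpatient tacrolimus trough levels) or an undetectable tacrolimus trough level". Incidence of meeting it is a secondary endpoint (Protocol 3.3). Protocol 8.4 sets a data minimum for the SD: "A rolling SD will be calculated for every patient using 1-year of tacrolimus levels (at least 3 trough levels". SAP 7.3.1 turns that minimum into the denominator of the whole endpoint, "Among subjects who have at least 3 outpatient tacrolimus trough levels collected that are at least 3 months" post-transplant, and counts the SD criterion only: "The proportion of subjects with an estimated standard deviation at any time of 2.0 ng/mL or greater will be reported". It does not name an undetectable level as a criterion or say how one enters the SD.

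**Call trigger.** In Protocol 8.4, besides the SD criterion, "an undetectable level or the absence of a tacrolimus trough level for 3 months will trigger a phone call". The heading of the call schedule in the same section (Table 10) says "following SD of 2.0 or more or undetectable level" and does not name absent levels.

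**Completion.** The SAP synopsis, like Protocol 3.3, gives the endpoint as "Percentage of participants meeting tacrolimus variability threshold who complete tacrolimus variability intervention". Protocol 13.2 words the denominator as those picked out for the intervention, with no condition of agreement. The analysis in SAP 7.3.1 reads: "Among subjects who qualified for and agreed to participate in the TVI, the proportion of subjects who complete the intervention".

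**The concern.** The third secondary objective (Protocol 1.3) is the feasibility of the phone intervention. Whether families take it up is part of that question. A completion rate confined to those who agreed answers a narrower question than the endpoint, and the SAP gives no reason for the change. The protocol conditions on agreement only for the change-in-SD analysis (Protocol 13.4.4), so the restriction may have been carried over from there.

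The threshold analysis has a similar gap. A child with one or two levels, one of them undetectable, meets the protocol definition but falls outside both the numerator and the denominator in SAP 7.3.1.

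**Working it through.** The documents state no expected rate, precision or sample size for these endpoints, so there is no figure of the plan's to reproduce. Every rate below is an assumption.

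**1. Completion**

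Let *q* be the number who meet the threshold, *r* the share of them who do not agree, and *c* the number who complete.

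- Protocol rate = *c*/*q*.
- SAP rate = *c*/[*q*(1 − *r*)] = protocol rate/(1 − *r*).

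For the same qualifiers the SAP rate is never lower. It is higher once one qualifier does not agree and at least one completes. The factor 1/(1 − *r*) is:

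| *r* | 10% | 20% | 30% | 50% |
|---|---|---|---|---|
| factor | 1.11 | 1.25 | 1.43 | 2.0 |

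With *q* = 20, about 80% completion among those who agree, and exact 90% intervals:

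| Not agreeing | Completed/agreed | SAP rate | Protocol rate |
|---|---|---|---|
| 0 | 16/20 | 80.0% (59.9–92.9) | 80.0% (59.9–92.9) |
| 4 (20%) | 13/16 | 81.3% (58.3–94.7) | 13/20 = 65.0% (44.2–82.3) |
| 10 (50%) | 8/10 | 80.0% (49.3–96.3) | 8/20 = 40.0% (21.7–60.6) |

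**2. Does the SD rule catch an undetectable level anyway?**

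Suppose a window holds *n* levels, one entered as 0 and the rest all equal to *m*. The sample variance is *m*²/*n*, so the SD is *m*/√*n*. It is at least 2.0 when *n* ≤ (*m*/2)².

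| *m* (ng/mL) | 6 | 8 | 10 | 12 |
|---|---|---|---|---|
| SD with *n* = 3 | 3.46 | 4.62 | 5.77 | 6.93 |
| largest *n* with SD ≥ 2.0 | 9 | 16 | 25 | 36 |

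These values of *m* lie within the target ranges in Protocol Table 3 for the period after week 2. The other levels are held constant here, which is the case least likely to reach 2.0. The cases lost are therefore mainly children with fewer than 3 levels, children with many levels in the window, and undetectable results dropped as non-numeric.

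**3. Direction for threshold incidence**

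Take all 50 randomized children as followed past 3 months, with 15 meeting the SD criterion.

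- All have at least 3 levels, and 2 or 5 more meet the threshold only by an undetectable level: SAP 15/50 = 30.0%; protocol definition 17/50 = 34.0% or 20/50 = 40.0%.
- Five have fewer than 3 levels and none is undetectable: SAP 15/45 = 33.3%; over all children 15/50 = 30.0%.
- Five have fewer than 3 levels and all five have an undetectable level: SAP 15/45 = 33.3%; protocol definition 20/50 = 40.0%.

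So the net bias can go either way. The second case runs upward only because 15/50 counts five children without a usable SD as not meeting the threshold. That convention has to be stated.

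**The case against.** Four replies deserve weight.

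*Missing levels.* A reader might infer that the SAP also departs from the endpoint by leaving out children with no level for three months. The documents do not support this. Absence of levels is a call trigger in the text of Protocol 8.4, but it is not in the threshold definition and not in the Table 10 heading. The protocol is inconsistent here, and omitting absence from threshold incidence follows the definition.

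*Undetectable levels.* A reader might infer that the SAP ignores them. That is too strong. Entered as a number, such a level usually meets the SD rule by itself, as the second step of the check shows. The SAP leaves their handling unspecified and drops them only as a stand-alone criterion. The minimum of 3 levels is also the protocol's own rule for computing the SD.

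*Feasibility.* A reader might infer that excluding children with few levels makes the intervention look more feasible, or that the least adherent are being removed. Neither is shown. The 3-level restriction acts on threshold incidence. The completion analysis rests on having qualified, which the SAP does not define and which may already include the other triggers. Nor are all non-participants decliners: Protocol 8.4 keeps inpatients and children excluded by investigator judgement out of the calls, and SAP 7.3.1 mentions children above 2.0 who were not flagged after enrolment into the intervention had ended.

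*A bare rate over all who met the threshold* would count children never offered calls as failures. This stands, and it is why the fix asks for a breakdown.

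It is also fair that these are descriptive secondary proportions, and that the SAP already plans to identify qualifiers who did not enrol. It uses them only as descriptive controls for the change in SD and plans no completion rate that includes them.

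**Conclusion.** The point holds on two counts.

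First, the completion denominator in SAP 7.3.1 contradicts the protocol endpoint and the SAP's own synopsis. For the same qualifiers it raises the reported rate by 1/(1 − *r*). If nobody declines there is no difference. The documents give no refusal rate, so the size is known only as a function of *r*: 1.11 times at 10%, 1.25 at 20%, 2.0 at 50%.

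Second, threshold incidence omits the undetectable-level criterion. The number of children affected cannot be fixed from the documents and is probably small where levels are plentiful and undetectable values are entered as numbers. The net bias in incidence has no fixed sign.

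Overstated feasibility follows from the completion denominator alone. This should be corrected, but it does not touch the primary endpoint.

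**What to change.** In SAP 7.3.1:

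- Count the threshold as met at the first of a rolling SD of 2.0 or more or any undetectable level.
- State how an undetectable value enters the SD.
- Show children with fewer than 3 levels and no undetectable result as a separate not-assessable count.
- Report completion among all who met the threshold as the endpoint. Beside it give the numbers not offered the intervention (including after its enrolment ended), excluded from calls under Protocol 8.4, declined, started and completed. Keep the rate among those who agreed as supplementary.
- Define what it means to qualify for the intervention and to complete it.
- Report three months without a level separately, as a call trigger.

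In the protocol, the Study Definitions page, the text of 8.4 and the Table 10 heading must be reconciled on whether absence of levels belongs to the threshold.

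The cost is wording and one flow table. The completion figure will be less favourable if anyone did not take part.
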